New Mothers. New mothers will be advised that if they consent to participate, they will receive support from peer counselors, information either via paper or mobile (text message and/or video using a mobile phone), and follow-up visits from peer counselors during the 6 months post-delivery. After consent, we will allow mothers to be contacted by one of the trained peer counselors.

Intervention and Data Collection Plan. Peer counselors will have a minimum of 9 visits with mothers. Visit 1 and 2 will occur prenatally at which time baseline data will be collected; initial BF education based on appropriate BEST4Baby content will also take place. The counselors will visit the new mothers within 3-5 days after delivery to obtain relevant data (e.g., when breastfeeding was initiated) and provide needed assistance in establishing BF. Another visit will occur again at two-weeks post-partum to record progress and offer support; remaining visits will be based on an agreed upon schedule. Information will be exchanged at visits and potentially between home visits. BF mothers may request additional visits and peer counselors will be available by phone to answer questions and address concerns. Data will be collected to determine usage of the BEST4Baby app during each visit. Standardized data collection sheets for the peer counselors will be developed; and counselors will be trained in writing field notes and documenting their impressions of the visit. At six months postpartum, research staff will query the mother about present and planned BF practices, environmental influences on breastfeeding, level of community support for BF, and overall satisfaction with the BEST4Baby program. At study conclusion, research staff will obtain feedback from the peer counselors on usability of the mHealth app.

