Comparison Cohort. To enable effect and sample size calculations, an appropriate comparison cohort will be used. We will obtain baseline and six-month post-partum data from a control group of 120 women delivering in facilities and living a suitable distance from study clusters to avoid contamination. A simple survey will be developed and administered by research staff to collect data comparable to that collected from mothers counseled (e.g., current BF practices and future intentions for continuation of breastfeeding). Women in this comparison cohort will provide informed consent and be provided with a small gift (e.g., a branded carrying bag) to show appreciation for their participation.

Month 24

Data Analysis. For survey, application utilization, and subject data associated with Specific Aim 2, we will conduct bivariate analyses (crosstabs, Chi-square procedures) to examine demographics and other measured variables potentially related to breastfeeding. Changes from baseline to follow-up in breastfeeding and other study outcomes and potential moderating variables (e.g., lifestyle changes due to childbirth and behaviors) will be examined.

We will also document engagement in and use of the BEST4Baby program by both the peer counselors and new mothers. The BEST4Baby program will collect usage data, (e.g., utilization, approximate time spent in use of application during home visits) in the follow-up interviews. These combined process measures will be calculated as a _dosage index' and used as a covariate in subsequent analyses. The dosage index will both 1) document process and 2) serve as an independent variable for multivariate modeling. Dosage measures will include time/counts of activity, intensity, engagement, and satisfaction, and will serve to document the feasibility of the BEST4Baby approach to train the peer counselors as well as to support new mothers to initiate and continue breastfeeding.

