Subjects that take the BEST4Baby training will take pre- and post-tests to assess if training increased breastfeeding knowledge; these women will also be asked to provide feedback relative to the acceptability of mHealth technologies and tools developed during the BEST4Baby program and to share perceptions about the perceived feasibility of continuing their use during an extended period of service as a counselor. Mothers will be recruited by research staff and asked to consent to being counseled during home visits and to providing data needed for purposes of BEST4Baby. Research staff will obtain feedback and ask questions to generate information about breastfeeding (e.g., when it was initiated, if exclusive breastfeeding occurred, how long any type of breastfeeding was maintained, and intent to continue breastfeeding beyond the close of BEST4Baby). A group of mothers not receiving peer counseling will also consent and serve as a comparative group to assess if breastfeeding practices are better among peer-counselled mothers compared to mothers not having peer counseling.

It is planned that data generated by the BEST4Baby formative research will be utilized for the design of a clinical trial that can generate definitive findings relative to the effectiveness of mobile technologies to promote optimal breastfeeding and to increase sustainability of a peer counselor model for delivery of breastfeeding support.

Describe the characteristics of the subject population, including their anticipated number, age range, and health status, if relevant. Focus groups will have 8-10 participants and all participants will consent before initiation of focus group discussions. At least two focus groups will be held for each target group described below, except that there will be at least one Target Group A focus group in each of the six clusters selected from among the clusters located within the larger JN Medical College Global Network study area for participation in BEST4Baby. Characteristics of focus group target groups follow.

Target Group A: This group will be comprised of mothers who have breastfed at least one child in the past three years. Other inclusion criteria include: 18 years of age, and willing to provide informed consent. To the extent feasible, mothers representing the diversity that exists in the cluster of residence will be encouraged to participate. A Target Group A focus group will be held in each of the 6 clusters participating in BEST4Baby.

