Pilot-testing requires recruitment of potential counselors and mothers willing to engage in interactions associated with BEST4Baby for a longer period of time, and length of retention from consent to the month prior to study closure will be monitored and noted. Additionally, it is hoped that women engaging in counseling and support of breastfeeding mothers will continue to perform these activities until project end (and ideally beyond). Mothers that are receiving counseling and support will hopefully not withdraw (despite their right to do so) from project participation so that most mothers having infants reaching six months of age before the 24th month of the study can be contacted to ask if they breastfed infants exclusively for six months post-delivery and about other infant feeding practices. Mothers having older babies before the 24th month of the project will be asked if breastfeeding was continued after their infant reached 6 and the introduction of complementary feeding. And prior to the end of BEST4Baby, we will also seek information from mothers still breastfeeding about their intent to continue breastfeeding. An improvement in breastfeeding exclusivity and breastfeeding duration higher than recently reported—baseline data for Karnataka (which can be found in the Rapid Survey of Children, Final Report for 2013-2014 issued by the Ministry of Women and Child Development, Government of India as of April 2016) will suggest that the tools utilized have the potential for influencing improved outcomes and provide the basis for the design of a subsequent clinical trial.

If relevant, explain the rationale or the involvement of special vulnerable populations, such as fetuses, neonates, pregnant women, children, prisoners, institutionalized individuals, or others who may be considered vulnerable populations. It is possible that pregnant women that have breastfed at least one child in the past three years could be included in focus groups for Target Group A, and some pregnant women will be recruited for the pilot-testing phase of the project. For research designed to explore how to improve breastfeeding exclusivity and duration, it is essential to involve such women. The exploratory research associated with BEST4Baby poses very low risks that are outweighed by the potential health advantages that could be realized by mothers and babies due to achievement of breastfeeding objectives.

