- Records with contact information and other necessary data to enable participation in research components of the project and the interactions with and between counselors recruited for breastfeeding education/training and mothers who will receive counseling and support during the pilot testing phase of the project

Describe any data that will be collected from human subjects for the project(s) described in the application. Data, primarily qualitative in nature, to be collected from human subjects is listed below.

- Data related to knowledge, attitudes, beliefs, behaviors, motivations, and barriers that influence breastfeeding practices
- Data useful for assessing if the peer counselor model is a feasible means for increasing exclusive breastfeeding and maintaining breastfeeding for the recommended period of time
- Data related to the barriers and facilitating factors for recruitment and retention of breastfeeding peer counselors
- Data that describes institutional needs for creating a successful peer counseling model and a successful culturally appropriate training curriculum
- Data relevant to the feasibility of using a mobile -based platform to support the peer counselor model for education, counseling and support of mothers
- Data relevant to the feasibility, acceptability and effect size of the BEST4Baby program o Survey data from mothers which includes socio-demographic data; data relevant to breastfeeding and support for breastfeeding; breastfeeding knowledge, attitudes, beliefs, and intentions to continue breastfeeding; and environment influences and factors that support breastfeeding
- Data relevant to the acceptability and use of breastfeeding mobile technology tools
- Names and contact information of subjects recruited to participate in components of the project

Data resulting from querying mothers receiving counseling/support during the pilot testing phase of the project based, for example, on questions related to if and when babies were breastfed exclusively, pre-lacteal feeds given to newborns, when breastfeeding was initiated and when it was stopped, when complementary feeding was initiated.

Indicate who will have access to individually identifiable private information about human subjects AND

Provide information about how the specimens, records, and/or data will be collected, managed, and protected, as well as whether any individually identifiable private information will be collected specifically for the proposed research project:

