Participation in the pilot due to the intervention presents minimal risks for consenting mothers or their newborns as the intervention--breastfeeding education and support—are generally considered to increase the probability that breastfeeding and other infant feeding practices will comply with recommendations of trusted health organizations. The key members of the research team are responsible for assuring that peer counselors are well-trained and committed to visiting mothers and carrying out their duties—e.g., providing accurate breastfeeding information and tips about proper technique and positioning, education about the benefits of exclusive breastfeeding until an infant reaches 6 months, emotional support as needed, and advice about care-seeking when the peer counselor becomes aware of a maternal or newborn health-related problem likely to require attention from a health care provider. During the pilot, it is expected that JNMC key personnel and [name], the pilot study coordinator, will meet at least monthly with the peer counselors providing the intervention. Additionally, peer counselors will complete a data form for each visit made to a mother. Ideally, the reporting form will be completed via cell phone/tablet and transmitted to data personnel at JNMC’s Research Unit; otherwise, peer counselors will complete a paper form and the forms will be provided at least every two weeks to the Research Unit. The Study Coordinator will review these forms on an ongoing basis and if he has any concerns, he will discuss concerns with JNMC key persons. Data from the forms will be entered in a data base and a report of the visits will be made available to key personnel of BEST4Baby (in India and the US) each month during the pilot until such time as official study visits between peer counselors and mothers end. When peer counselors complete the form, they will not use a subject’s name but rather a study identification number assigned to the mother at the time of consent. Additionally, each counselor will use a study identification number when reporting. Thus, the monthly reports will not include names, but visit data may be aggregated and summarized in a manner to associate the data with a specific peer counselor identified by identification code. Although the data form may contain data relevant to status of breastfeeding, this data will not be included in the monthly monitoring report as the purpose of these reports is primarily to determine if the peer counselors conducted visits consistent with the protocol and used educational tools provided to them, and if they encountered any unanticipated problems.

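### Exclusive breastfeeding at six months is described only by its label, with no rule for classifying it, so the counselled-versus-comparison difference may mix changed feeding with changed answers

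*Combined protocol and SAP*

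**What the plan says.** The protocol describes how EBF is obtained in three places, each time by its name.

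- Section I.a, in the paragraphs on sampling and retention: mothers with infants reaching six months "can be contacted to ask if they breastfed infants exclusively for six months post-delivery", and will also be asked about other infant feeding practices.
- Section I.a, earlier: research staff will seek information such as "if exclusive breastfeeding occurred, how long any type of breastfeeding was maintained".
- Section II, Sources of Materials: for counselled mothers, "questions related to if and when babies were breastfed exclusively, pre-lacteal feeds given to newborns, when breastfeeding was initiated and when it was stopped", and when complementary feeding began.

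For comparison mothers, the Comparison Cohort paragraph says: "A simple survey will be developed and administered by research staff to collect data comparable to that collected from mothers counseled". Its examples are current practices and future intentions.

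The intervention teaches the concept being measured. Section VI lists among the counsellors' duties "education about the benefits of exclusive breastfeeding until an infant reaches 6 months". The Intervention and Data Collection Plan sets a minimum of nine visits, two of them prenatal. Its six-month interview by research staff covers feeding practices and also "overall satisfaction with the BEST4Baby program".

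The specific aims make a rise in the six-month EBF rate a secondary outcome. Objective 2.2 is to assess an effect size against the comparison mothers, and the Conclusion says the findings will support an application for a fully powered trial.

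**The concern.** A mother's answer about exclusivity depends on what she fed her infant, what she takes the term to mean, and what answer she thinks is wanted. The intervention is designed to change the first and may also change the other two. Teaching the recommendation can make a non-exclusive mother readier to say yes. Teaching that water or a prelacteal feed breaks exclusivity can make her readier to say no, while an untaught mother who gave water may say yes in good faith. The two mechanisms push the group difference in opposite directions.

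This is separate from whether the question covers the whole six months or current feeding. It would remain if both groups were asked an identically worded label question about the same period. A larger sample does not reduce it, and neither the bivariate chi-square analyses nor the exact logistic models on dosage (Month 24) can separate it from a real change in feeding. Any such error would pass into the effect size used to design the next trial.

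**Working it through.** **The plan's own figure.** Six clusters x 4 counsellors = 24, and 24 x 5 mothers = 120 counselled, as stated. The comparison group is 120 in the specific aims, the Comparison Cohort paragraph and Section I.a; one paragraph of I.a prints 12, and 120 is used here. The documents give no alpha, power or target difference, so there is no power calculation to reproduce.

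**Assumptions.** None of these comes from the documents: true EBF rate p of 30%, 50% or 70%; all truly exclusive mothers answer yes; a share f of non-exclusive mothers also answers yes (the false-yes rate); two-sided 5% test; independent mothers; no dropout.

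**Formulas.** Reported rate = p + f(1 - p). With no true effect, the false difference = (1 - p) x (f counselled - f comparison). The chance of p<0.05 is Phi[(|d| - 1.96 SE0)/SE1], where d is the reported difference and SE0 and SE1 are its pooled and unpooled standard errors with 120 per group.

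**No true effect, f = 10% in the comparison group**

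| True EBF | f counselled | Reported rates (comparison, counselled) | False difference | Chance of p<0.05 |
|---|---|---|---|---|
| 30% | 20% | 37%, 44% | +7 points | 20% |
| 30% | 30% | 37%, 51% | +14 points | 59% |
| 50% | 20% | 55%, 60% | +5 points | 12% |
| 50% | 30% | 55%, 65% | +10 points | 35% |
| 70% | 20% | 73%, 76% | +3 points | 8% |
| 70% | 30% | 73%, 79% | +6 points | 19% |

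Worked case, second row: SE0 = sqrt(2 x 0.44 x 0.56/120) = 0.0641; SE1 = sqrt((0.37 x 0.63 + 0.51 x 0.49)/120) = 0.0634; (0.14 - 1.96 x 0.0641)/0.0634 = 0.23; Phi = 0.59.

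**Rates reversed (30% comparison, 10% counselled) with a true gain of 20 points.** Reported difference = 0.20 x (1 - 0.10) - (1 - p) x (0.30 - 0.10).

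- From 30%: 0.18 - 0.14 = +4 points, an understatement of 16. Power falls from 89% to 9%.
- From 50%: 0.18 - 0.10 = +8 points, an understatement of 12. Power falls from 89% to 27%.

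**Equal error for contrast (10% in both groups).** No true effect is reported as 0, and a true 20 points as 0.20 x 0.90 = 18. So 2 points of each understatement above are ordinary dilution, and the other 14 or 10 come from the difference between groups.

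**Lower true rates.** The bias grows as true EBF falls. At 20%, the 10% versus 20-30% pattern gives 0.80 x 0.10 = 8 to 0.80 x 0.20 = 16 points.

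**The case against.** The strongest reply is that the protocol contains no questionnaire. The comparison survey has yet to be developed, and the three passages state what information is wanted, not how items are worded. A reader might infer that mothers will be asked a single question using the word exclusive. The documents do not establish that, and the text is compatible with itemised questions. This part of the reply stands, but nothing commits the study to itemising. Section II names prelacteal feeds and the start of complementary feeding, but for counselled mothers only, without water or other liquids, and not as part of an EBF definition. The Data Analysis section separates exclusive feeding, mixed feeding and milk substitutes without saying how mothers are assigned to each.

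A reader might also infer that only counselled mothers learn the term. The documents contradict that: the Significance section describes a national programme (MAA) of counselling through families and health facilities, comparison women deliver in facilities, and the Innovation section says ASHAs may support breastfeeding. That narrows the contrast. The protocol still adds at least nine visits to one group only.

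It is also fair to say that the false-yes rates have no source, that the opposing mechanisms could cancel, that satisfaction comes last in the list of interview topics, and that EBF is a secondary outcome in a non-randomised exploratory pilot. These points limit the weight of the concern but do not remove it.

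**Conclusion.** The concern holds in a limited form. The six-month EBF outcome is named but not defined, and its meaning and desirability are part of what one group is taught. The group difference may therefore include a reporting difference of unknown size and sign. The documents do not show that the intervention will cause such misclassification, or that it would inflate the effect.

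Under the assumed false-yes rates, the false difference is 3-14 points over true EBF of 30-70%, significant in about 8-59% of studies. In the reverse pattern, a true 20-point gain from 30% or 50% is understated by 16 or 12 points. These figures illustrate what is possible and do not estimate what will happen. The change should be made, because the estimate is intended for a later trial and the survey is not yet written.

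**What to change.** In both groups, have research staff ask the same itemised questions on water, other milk, formula, prelacteal feeds, other liquids and solids: whether each was ever given, the infant's age when it was first given, and a previous-day list. Put these items before any programme or satisfaction question. State in the protocol one fixed rule that classifies EBF from the answers, and apply it identically to both groups. Keep the label question as a secondary item and report its agreement with the itemised status by group, which shows how far understanding of the label differs.

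The cost is a few more survey lines, and the reported EBF rate may be lower than the label would give. State as a limitation that itemising reduces misunderstanding of the term but does not remove socially desirable answers: a mother taught that water breaks exclusivity can still deny giving it. The equal-error result in the working is therefore a best case, not a promise.

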Breastfeeding, a natural and safe means of feeding infants, provides nutritional, immunologic, psychological and economic benefits with recognized and unquestionable advantages. Human milk is a complex —species-specific biological fluid, adapted throughout human existence to perfectly satisfy the nutritional and immunological needs of the child⁵. For many years BF has been known to be an important intervention in developing countries to reduce mortality from infectious diseases and malnutrition³. However, only 39% of all infants worldwide receive EBF, even when the assessment is made in children less than four months of age^{18,19}. Factors such as maternal age >35 years, nulliparity, low birth weight, resuscitation, and delivery by caesarean section contribute to the lack of EBF in settings found in India, where infant and young child feeding practices are not optimal. Studies in India show that EBF drops rapidly from the first month to the sixth month by which time only 20% of children are still being breastfed²⁰

Most national and international organizations that monitor health outcomes strongly recommend breastfeeding. Since May 2002, the World Health Organization and UNICEF have jointly developed and supported the Global Strategy for Infant and Young Child Feeding to revitalize global attention on the impact of feeding practices for improving child survival, growth and development. In 2011, the Breast Feeding Promotion Network of India initiated a plan to enhance the practice of BF in the country. The action plan suggested the opening of resource centers, counseling services and communication campaigns²⁰. In August 2016, India launched a nationwide program, Mother's Absolute Affection (MAA), to bring undiluted focus on the promotion of BF and to ensure that mothers receive counseling and support by family members and at health facilities. The BEST4Baby program will build upon both these initiatives while focusing on the implementation and sustainability of utilizing peer counselors for breastfeeding support using an mHealth app.

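### The pilot's effect size has no adjusted, cluster-aware group analysis behind it, and one sentence lets an older state survey stand in as the yardstick

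*Combined protocol and SAP*

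**What the plan says.** **The objective.** Objective 2.2, under Primary Aim 2, sets 120 counselled mothers against 120 uncounselled mothers to assess effect size. The Comparison Cohort paragraph and section I.a give the comparison group the same role. EBF at 6 months is described as a secondary outcome. Section I.a states that assignment is not random: it depends on where a woman lives.

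**The analysis (Specific Aim 2, Month 24, Data Analysis).** Four elements are planned:
- Bivariate work: "we will conduct bivariate analyses (crosstabs, Chi-square procedures) to examine demographics and other measured variables potentially related to breastfeeding".
- Change over time: "Changes from baseline to follow-up in breastfeeding and other study outcomes and potential moderating variables" will be examined.
- A dosage index that will "serve as an independent variable for multivariate modeling". On its content: "Dosage measures will include time/counts of activity, intensity, engagement, and satisfaction".
- Exact logistic regression of 6-month feeding outcomes on dosage.

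Group is not named as a model term. No confounders are listed, no interval is mentioned, and neither cluster nor counsellor appears.

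**The external yardstick (section I.a, sampling plan and retention).** "An improvement in breastfeeding exclusivity and breastfeeding duration higher than recently reported" for Karnataka in a 2013-14 government survey "will suggest that the tools utilized have the potential for influencing improved outcomes and provide the basis for the design of a subsequent clinical trial". The survey rate is not given. On timing, the Significance section says: "In August 2016, India launched a nationwide program" to promote breastfeeding.

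**The concern.** The protocol's conclusion says the findings will feed an application for a fully powered trial. An effect size used that way needs a defined contrast, some control of confounding and an interval that is not too narrow.

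The first risk lies in the group contrast. A chi-square test of group by feeding would be a crude comparison of different areas. The Background section itself lists maternal age, parity, education and family type as influences on feeding. The test would also count mothers from the same cluster as independent.

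The second risk lies in the survey sentence. It supports a favourable reading without reference to the concurrent group. The survey predates the national programme, so rates may have risen in the meantime for reasons unrelated to BEST4Baby. A different mix of mothers could have the same effect.

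**Working it through.** **1. The plan's own figure.** 6 clusters × 4 counsellors = 24, and 24 × 5 mothers = 120 counselled mothers, which reproduces. That is 20 mothers per cluster and 5 per counsellor. The comparison group is taken as 120, as in objective 2.2, the Comparison Cohort paragraph and the subject-population text. The figure of 12 in the assignment text of section I.a looks like a typing error. No power, alpha, target difference or ICC is stated, so there is nothing further to reproduce.

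**2. Which planned analysis can deliver the EBF contrast?**

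| Planned analysis | Can it give counselled v comparison for EBF at 6 months? |
|---|---|
| Crosstabs, chi-square | Yes, but unadjusted and assuming independence |
| Change from baseline | No. Counselled mothers' baseline is prenatal (Intervention and Data Collection Plan), so the study infant has no baseline EBF |
| Dosage models | No. The index comes from programme activity, engagement and satisfaction, which comparison mothers lack |

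**3. Precision of the contrast (illustration).** Assumed: equal rates of 20% or 39%, no dropout, six clusters of 20 in each group, and ICC 0.01 to 0.10. The number of comparison clusters, the ICC and the local rate are not in the documents. The two rates only bracket a range. In the Significance section, 39% is a worldwide EBF figure assessed in infants under four months, and 20% is an Indian figure for the sixth month.

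- Independent mothers: half-width = 1.96 × √(2p(1−p)/120). At 20%, 1.96 × 0.0516 = 10.1 points. At 39%, 1.96 × 0.0630 = 12.3 points.
- Clustered: design effect = 1 + (20−1) × ICC, and t on 12 − 2 = 10 df (2.228) replaces 1.96.

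| ICC | Design effect | Half-width at 20% | Half-width at 39% | True type I error of an uncorrected 5% chi-square |
|---|---|---|---|---|
| 0.01 | 1.19 | 12.5 | 15.3 | about 7% |
| 0.05 | 1.95 | 16.1 | 19.6 | about 16% |
| 0.10 | 2.90 | 19.6 | 23.9 | about 25% |

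The last column is 2 × (1 − Φ(1.96/√design effect)).

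**4. The survey yardstick (illustration).** Take one indicator, 120 independent mothers, a survey rate known without error and no programme effect. The exact binomial probability that the observed rate exceeds the survey rate is:

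| Assumed survey rate | Local rate unchanged | Local rate already 5 points higher |
|---|---|---|
| 20% | 0.446 | 0.878 |
| 40% | 0.460 | 0.844 |
| 60% | 0.465 | 0.854 |

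The documents name exclusivity and duration together and give no margin or test, so this shows how weakly such a yardstick discriminates. It is not the operating characteristic of a stated rule.

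**5. Number evaluable.** The plan hopes that "most mothers having infants reaching six months of age before the 24th month of the study can be contacted". The pilot runs over months 15-23, so reaching six months by the end of month 23 requires birth by the end of month 17. If births were spread evenly over the nine months (assumed), 120 × 3/9 = 40 per group would qualify. At 39%, the half-width would then be 21.4 points for independent mothers. With ICC 0.05 and 10 df (design effect 1 + (40/6 − 1) × 0.05 = 1.28) it would be 27.5.

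**The case against.** The strongest reply is that this is an exploratory pilot. Its primary outcome concerns training and support of counsellors, EBF is secondary, no confirmatory test is promised, and definitive inference is left to a later trial with a somewhat different question. This stands, and it limits the weight of the point. It does not remove it, because estimating an effect size is one of the pilot's own objectives.

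A second reply is that the comparison is already specified. A reader might infer from the Month 24 text that no between-group comparison is planned. The documents do not support that: objective 2.2 names both groups, the Comparison Cohort paragraph states the purpose, and a group-by-feeding crosstab is a natural reading. What is missing is the estimator, the adjustment and the handling of clusters.

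A third reply concerns the survey sentence. A reader might take it as a go/no-go rule that bypasses the comparison group. Its wording is soft, it sits in a paragraph on retention, and other sections assign the assessment of counselling to the comparison group. It remains a loose statement that should be corrected.

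Fourth, change from baseline is sound for knowledge, attitudes and intentions, which can be measured prenatally. The limitation applies only to EBF of the study infant.

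Finally, a reader might infer that only about 40 mothers per group will be evaluable. That follows solely from assuming evenly spread births. Women may enrol at any point in the third trimester, and the planned six months of visits favours early enrolment.

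**Conclusion.** The concern holds in a limited form. The comparison is planned, but the only listed analysis able to deliver it for EBF at 6 months is unadjusted and assumes independence, in a design where group is fixed by cluster of residence. Followed as written, this would pass a confounded and over-precise effect size to the next trial's planning. The sentence on the 2013-14 survey adds a second, weaker basis that a background trend could satisfy.

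On the stated assumptions (equal rates, 120 per group, six clusters of 20 per group, ICC 0.05, 10 df), the half-width rises from 10.1 to 16.1 points at 20%, or from 12.3 to 19.6 at 39%. The conclusion rests on the text of the plan. The figures only show scale, since the ICC, the Karnataka rate and the number of comparison clusters are not stated. The change should be made, but the pilot can run without a confirmatory analysis.

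**What to change.** 1. **Section I.a, retention text.** Base the conclusion on the counselled-minus-comparison difference in EBF at 6 months with its 95% interval. Keep the state survey as descriptive context only.
2. **Month 24 Data Analysis.** Name that contrast as the effect-size analysis: a risk difference with a group term, adjusted for a short set of maternal characteristics from the Background section. Parity and education would do, with age and family type added if numbers allow. Collect them the same way in both groups.
3. **Interval.** Allow for clustering by study cluster with a small-sample correction (t with total clusters minus 2 df). An exact logistic model stratified on cluster would not serve, because group does not vary within a cluster. State the number of comparison clusters, and report the number evaluable at 6 months in each group.
4. **Dosage models.** Keep them as a secondary analysis within counselled mothers.

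The cost is some wording, a few items in a comparison survey that is still to be developed, and a visibly wider interval. No change to recruitment or to the intervention is needed.
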